**AbbVie AG (AbbVie)**

**Post Marketing Observational Study**

**Protocol P16-272**

**Quality of Life measurement using wrist  
actigraphy in HCV genotype 1 infected,  
treatment naïve patients suffering from  
fatigue and receiving ombitasvir, paritaprevir, and  
ritonavir tablets and dasabuvir tablets  
(Viekirax®/Exviera®; 3D regimen):  
The HEMATITE Study**

Product Name:	ombitasvir, paritaprevir, and ritonavir tablets and dasabuvir tablets (Viekirax ® /Exviera ® ; 3D regimen)
Type of Study:	Observational Study
Status of Document:	V1.0
Date:	20 September 2016
Sponsor	AbbVie AG, Switzerland

**This study will be conducted in compliance with this protocol.  
Confidential Information. No use or disclosure outside AbbVie is permitted without prior written**

Title	Quality of life measurement using wrist actigraphy in HCV genotype 1 infected, treatment naïve patients suffering from fatigue and receiving ombitasvir, paritaprevir, and ritonavir tablets and dasabuvir tablets (Viekirax ® /Exviera ® ; 3D regimen): The HEMATITE Study
Protocol Version Identifier	P16-272
Date of Last Version of Protocol	20 September 2016
EU PAS Register Number	Not Applicable
Active Substance	Ombitasvir, paritaprevir, and ritonavir tablets; dasabuvir tablets (Viekirax ® /Exviera ® ; 3D regimen)
Medicinal Product	Ombitasvir, paritaprevir, and ritonavir tablets; dasabuvir tablets (Viekirax ® /Exviera ® ; 3D regimen)
Product Reference	Not Applicable
Procedure Number	Not Applicable
Marketing Authorization Holder(s)	AbbVie AG Schweiz [name]
Joint PASS	Not Applicable
Research Question and Objectives	To observe the impact of the 3D regimen on total daytime physical activity in Hepatitis C Virus (HCV) positive patients in a real-world setting. Objectives: 
 
• To observe changes in physical activity (assessed by means of an electronic wrist-worn activity tracker) in patients with newly initiated 3D regimen before, during and after treatment,
 
• To correlate subjective fatigue (assessed by means of the validated FSS (Fatigue Severity Scale) questionnaire) and physical activity,
 
• To observe the proportion of patients achieving sustained virologic response 12 weeks after end of treatment with 3D (SVR12).
 

## 2.0 Abbreviations

3D regimen	Ombitasvir, Paritaprevir, and Ritonavir tablets (Viekirax ® ); Dasabuvir tablets (Exviera ® )
AASLD	American Association for the Study of Liver Diseases
AE	Adverse Event
BMI	Body Mass Index
CA	Competent Authorities
CHCV	Chronic Hepatitis C infection, defined as the presence of detectable viral replication for at least six months.
CNS	Central Nervous System
CRF	Case Report Form
CRO	Contract Research Organization
EASL	European Association for the Study of the Liver
EC	Ethics Committee
EMA	European Medicines Agency
EOT	End of Treatment
FSS	Fatigue Severity Scale
HCV	Hepatitis C Virus
ICMJE	International Committee of Medical Editors
LSLV	Last Subject Last Visit
MAH	Marketing Authorization Holder
PMOS	Post Marketing Observational Study
QoL	Quality of Life
RBV	Ribavirin
RNA	Ribonucleic acid
SAE	Serious Adverse Event
SAP	Statistical Analysis Plan
SmPC	Summary of Product Characteristics
SVR	Sustained Virologic Response
SVR12	Sustained Virologic Response at 12 weeks after EOT
V	Visit
WHO	World Health Organization

## 4.0 Abstract

**Title:** Quality of life measurement using wrist actigraphy in HCV genotype 1 infected, treatment naïve patients suffering from fatigue and receiving ombitasvir, paritaprevir, and ritonavir tablets and dasabuvir tablets (Viekirax®/Exviera®; 3D regimen): The HEMATITE Study

**Background and Rationale:**

Physical and mental fatigue is the most common symptom reported by patients with Hepatitis C Virus (HCV), which highly impacts their overall quality of life. AASLD (American Association for the Study of Liver Diseases ) and EASL (European Association for the Study of the Liver) guidelines therefore rate the treatment of HCV patients suffering from debilitating fatigue as a high priority. This cardinal symptom presents regardless of the stage of liver fibrosis and is difficult to quantify objectively. Similar to other potential reasons for physical fatigue, such as hepatic encephalopathy, increasing evidence suggests a direct viral impact on the central nervous system (CNS). Data demonstrating a longitudinal change of debilitating physical fatigue and increased daytime physical activity upon treatment with 3D regimen are missing to date and are anticipated by the Swiss scientific HCV community [1, 2].

The rationale for this observational study is to observe the impact of therapy with 3D regimen on physical activity of HCV patients suffering from debilitating fatigue. Furthermore, this study supports the Swiss Hepatitis Strategy, which seeks for the elimination of viral hepatitis in Switzerland within the next 15 years by creating awareness for patients with extrahepatic manifestations [3].

**Research Question and Objectives:**

Does successful treatment with 3D regimen increase total daytime physical activity and reduce fatigue in HCV-positive patients?

Primary objective:

- To observe changes in physical activity in patients with newly initiated therapy with 3D regimen between pre-treatment (baseline) and post-treatment week 12

Secondary objectives:

- To correlate subjective fatigue (assessed by means of Fatigue Severity Scale [FSS]) and physical activity (measured with an electronic activity tracker) at baseline, during and after 12 weeks of treatment with 3D regimen
- To observe the proportion of patients achieving sustained virologic response (SVR12) after treatment with 3D regimen (defined as HCV not detectable, 12 weeks after the last dose of 3D regimen)
- To observe sleep efficiency (assessed by means of activity tracker) at baseline, during and after 12 weeks of treatment with 3D regimen

**Study Design:**

This is an observational, prospective, open label, single-arm, multi-centric, real-life study in HCV-positive patients (genotype 1).

The study consists of a treatment preparation phase of 4 weeks to obtain baseline physical activity by use of a wrist-worn activity tracker, a treatment phase (12 weeks) and a follow-up phase (12 weeks) to evaluate treatment response. The activity tracker is worn for 4 weeks before each visit, to obtain stable individual activity data. At every visit, questionnaire-based fatigue is recorded (FSS questionnaire), according to routine clinical care.

**Population:**

Patients are eligible for observation in this study, if the following applies:

**Inclusion Criteria:**

- Male and female patients aged  $\geq 18$  years
- Treatment-naïve patients
- Patients monoinfected with CHCV, GT1 (confirmed within the last 36 months or at physicians discretion in case of risk factors)
- Non-cirrhotic patients (based on liver biopsy, fibroscan  $\leq 9.6$ kPa and/or clinical signs)
- The decision to treat with 3D regimen is made by the physician in accordance with the local Swiss product label prior to any decision to approach the patient to participate in this study. [4]
- Patients with debilitating fatigue (FSS  $\geq 4$ )
- Patients willing to participate in the study, and willing to wear an activity tracker

**Exclusion Criteria:**

- Patients with sources of fatigue other than HCV (especially, severe depression (Annex 4), cancer and hormonal disorders causing clinically significant fatigue)
- Patients with conditions that do not allow to adhere to protocol and use of the device at investigator's discretion
- Patients being wheelchair dependent

---

**Variables:**

Primary Variable

- Change of mean daytime physical activity between baseline (before treatment start) and post-treatment week 12

Secondary Variables

- Change of Fatigue Severity Score (FSS) between baseline, during and after 12 weeks of treatment with 3D regimen
- Correlation between mean daytime physical activity and FSS at baseline, during and after 12 weeks of treatment with 3D regimen
- Proportion of patients achieving SVR12 after treatment with 3D regimen (defined as HCV RNA not detectable 12 weeks after the last actual dose of 3D regimen)
- Sleep efficiency at baseline, during and after 12 weeks of treatment with 3D regimen

**Data Sources:**

Source documents are defined as original documents. The investigator will document patient data, including FSS, in his/her own patient files which will serve as source data for the study. Physical activity and sleep data will be collected by use of wrist-worn activity trackers (ActiGraph GT9X Link) which will be processed by device-specific software (ActiLife 6) to obtain the activity and sleep-related variables for analysis (Annex 1). All data collected by the activity tracker will be analyzed by the biostatistician at the end of the study. The data will not be seen by the investigators and patients at any time during data collection (between visit 1 and visit 5 (Figure 1: Study Activities)).

**Study Size:**

Approximately 100 patients in Switzerland will be enrolled.

**Data Analysis:**

All data will be analyzed by descriptive statistical methods. The correlation between physical

activity (assessed by the activity tracker) and the fatigue score (assessed by FSS) by visit, and the changes between baseline and the respective follow-up visits will be investigated by Spearman's rank correlation coefficient, supported by subgroup analyses. Two-sided 95% confidence intervals will be provided for primary and secondary endpoints, if applicable.

Details of planned analyses will be described in a separate statistical analysis plan (SAP).

**Milestones:**

Start of Data Collection: 01 January 2017

Last Patient first Visit: 31 December 2017

Final Report of Study Results: 30 June 2019

## 5.0 Amendments and Updates

None

## 6.0 Milestones

Major study milestones and their planned dates are as follows:

Start of Data Collection:	01 January 2017
Last Patient first Visit	31 December 2017
Final Report of Study Results:	30 June 2019

## 7.0 Background and Rationale

### Background

Hepatitis C virus (HCV) infection is one of the most common liver diseases worldwide. Approximately 2% of the global population suffer from chronic HCV infection. In the majority of cases, HCV infection leads to chronic hepatitis [5]. While several genotypes of HCV exist, genotype 1 is the most common genotype in Europe, comprising the majority of infections [6]. HCV replicates as well within extrahepatic tissues and causes a wide range of extrahepatic manifestations. In fact, 40-74% of patients infected with HCV develop at least one extrahepatic manifestation during the course of their disease [7]. Over the recent years, studies have demonstrated that HCV infection can directly cause cognitive impairment, even in the absence of liver cirrhosis [8, 9]: The biological effect of HCV on the brain may result from viral penetration of the central nervous system (CNS) and/or central neuroinflammation leading to alterations in cerebral metabolism, immune activation, and neurotransmission [10, 11].

There are several potential reasons for the high prevalence of neuropsychological disorders in patients with HCV: Individuals with a pre-existing mental illness have been hypothesized to be more likely to contract HCV, or to abuse psychoactive substances affecting cognitive performance [12, 13]. Another predisposing factor may be pharmaceutical HCV treatment, which can trigger neuropsychological disorders [14]. However, an increasing body of evidence suggests a direct

biological effect of HCV infection resulting in brain dysfunction, which may improve following eradication of the virus [10, 11]. Finally, the hepatic function impairment (cirrhosis) may lead to minimal or overt encephalopathies with a broad range of neuropsychological symptoms [15].

Clinically, HCV infection is strongly associated with multiple psychiatric comorbidities. Fatigue, i.e. sensations of both mental and physical exhaustion [16], is the most common symptom reported by patients with HCV [17, 18], which paradoxically may occur as well in conjunction with sleep disturbances, such as insomnia [19]. Fatigue can range from mild to severe and can affect every area of life. Conclusively, American and European guidelines (American Association for the Study of Liver Diseases [AASLD], European Association for the Study of the Liver [EASL]) rank the treatment of HCV-related debilitating fatigue as a high priority [20, 21]. Importantly, this symptom is difficult to quantify objectively and occurs independently from severe liver damage. In addition, there is a lack of controlled studies investigating fatigue in HCV patients [22]. Specifically on the effect of 3D regimen, there is a data gap on the association of treatment success and the improvement of fatigue.

Therapy of HCV has seen huge progress in recent years. Viekirax® (ombitasvir/ paritaprevir/ ritonavir tablets) is indicated in combination with Exviera® (dasabuvir tablets) with or without Ribavirin (RBV) for the treatment of chronic hepatitis C in adults, genotype 1. Combination treatment (3D regimen) combines three different antiviral mode of action and has been shown to result in sustained virologic response (SVR) rates higher than 95 percent [23-25].

### **Rationale**

Data demonstrating a longitudinal change of debilitating physical fatigue, along with concurrently increased daytime physical activity upon treatment with 3D regimen are missing to date and are highly anticipated by the Swiss scientific HCV community.

Furthermore, this study attempts to support the widely discussed Swiss Hepatitis Strategy, which seeks for the elimination of viral hepatitis in Switzerland within the next 15 years by creating awareness for patients with extrahepatic manifestations [3].

## **8.0 Research Question and Objectives**

### **8.1 Research Question**

Does successful treatment with 3D regimen increase total daytime physical activity and reduce fatigue in HCV-positive patients?

### **8.2 Objectives**

#### **8.2.1 Primary Objective**

- To observe changes in physical activity in patients with newly initiated therapy with 3D regimen between baseline (before treatment start) and post-treatment week 12

#### **8.2.2 Secondary Objectives**

- To correlate subjective fatigue (assessed by means of FSS) and physical activity (measured with an electronic activity tracker) at baseline, during and after 12 weeks of treatment with 3D regimen
- To observe the proportion of patients achieving sustained virologic response (SVR12) after treatment with 3D regimen (defined as HCV RNA not detectable, 12 weeks after the last dose of 3D regimen)
- To observe sleep efficiency (assessed by means of activity tracker) at baseline, during and after 12 weeks of treatment with 3D regimen

## **9.0 Research Methods**

### **9.1 Study Design**

This prospective, multicenter, post-marketing observational study (PMOS) will be conducted with a single arm design on HCV patients receiving 3D regimen according to routine clinical practice. This study will be conducted in the main Swiss HCV competence centers.

---

The decision of the treatment regimen is at the discretion of the physician in accordance with local clinical practice and label; it is made independently from this observational study, and precedes the decision to offer the patient the opportunity to participate in this study.

Adult patients diagnosed with HCV, for which the decision to treat with 3D regimen has been made, will be offered the opportunity to participate in this study during a routine clinical visit at the participating sites.

[figure not shown]
After written informed consent has been obtained, patient data including demographic data, HCV disease characteristics (including questionnaire-assessed fatigue), comorbidities, concomitant medication, and treatment details as recorded in the patient's medical records (source documentation) will be documented in the case report form (CRF).

Follow-up visits, treatment, procedures and diagnostic methods will follow physicians' routine clinical practice. Patients will be observed for approximately 28 weeks. No patient identifiable information will be captured; a unique patient number will be specified in the CRF.

The study activities to be conducted are outlined in the schematic presented below.

**Figure 1: Study Activities**

### 9.1.1 Description of Activities

Patients will be screened to ensure they meet the inclusion criteria. All patients will be required to sign an informed consent to use and disclose personal health information. By signing this consent, patients agree to release their information to AbbVie. No study related activity will be performed prior to obtaining written informed consent.

When the investigator has determined that the patient is eligible for participation, and the patient has agreed to be included in this observational study, the patient will be handed out his personal activity tracker (ActiGraph GT9X Link [26]) (Figure 1) and will be instructed in its use. The patient will be advised to report any potential side effects related to the activity tracker, such as possible discomfort wearing the device around the clock or possible skin rash or skin irritation, to the study personnel. ActiGraph GT9X Link has a data storage capacity of 240 days/4GB. Therefore, the patient will keep the tracker for the whole duration of the study (196 days). The patients will be requested to start wearing their activity trackers on the non-dominant arm constantly for 8 weeks between visit 1 and visit 3 and for 4 weeks preceding visits 4 and 5. Everytime the patient has to put on his tracker, he will receive a reminder call from a local study personnel to increase adherence. At the last visit, the investigator will collect the tracker and deliver it to the biostatistician which in turn transfers the activity data to a post-processed environment (ActiLife 6 [27]) (Figure 1).

If the investigator sees the medical indication to initiate treatment with 3D regimen before the patient has worn the activity tracker for at least 4 weeks during the treatment preparation phase, or if 3D regimen is discontinued at the investigator's discretion, the patient will discontinue study participation. ActiGraph GT9X Link comes with a wear time sensor that automatically detects if a wrist worn device has been removed. Thus, patient compliance to the tracker will be measured by this wear time sensor. If values are missing for a total of  $\geq 2$  hours during daytime, this day will be declared as non-eligible. In order to complete the data set of 2 weeks (10 working days) any non-eligible day will be replaced by daytime values in a pre-defined order, starting with the most recent day of the respective foregoing week (Figure 1). Weekend days are excluded from analysis.

## **Health Outcomes Assessment**

### Activity Tracker: ActiGraph GT9X Link (Annex 1) [26]

The ActiGraph GT9X Link has been classified as Class I medical device within the European Union and allows to deliver valuable information about movement, rotation, and body position.

---

There have been already published several examples of the use of ActiGraph devices in research studies and clinical trials involving physical activity, energy expenditure, and sleep/wake behavior and their relationships to a wide range of health conditions including HCV, obesity, diabetes, cancer, CNS disorders, cardiovascular disease and sleep disorders. [\[28-37\]](#).

The collected activity data can be utilized in a post-processed environment (ActiLife 6). Data is automatically collected from all on-board sensors in raw data format (Annex 1).

After a profound training on the tracker (activity monitor, software ActiLife 6) the local study personnel will be in charge to help and instruct patients correctly in the use and requirements to stay in the study, as well as to assist in the case of tracker-related questions that may arise. Furthermore, a detailed patient information brochure will give useful information about the tracker handling to the patient.

#### Questionnaire

Patients will be asked to complete the Fatigue Severity Scale (FSS) before treatment start and at each visit as part of routine practice. The FSS is a nine-item questionnaire assessing the functional impact of fatigue during the past two weeks on multiple life domains using scales from 1 (strongly disagree) to 7 (strongly agree). The fatigue score is the mean score of the 9 items. Clinically significant fatigue is usually defined as score equal or above "4" [\[38, 39\]](#). The routinely assessed FSS score to be used within this study should not include questionnaire results older than 3 months before visit 1. Patients with an average FSS score < 4 at visit 2 will discontinue study participation.

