### 9.1.4 Termination Criteria

A patient may withdraw from the study at any time. The investigator may discontinue any patient's participation for any reason. AbbVie AG may interrupt/stop the study at any time for any reason.

If a patient withdraws or is lost to follow-up, the reason for withdrawal will be recorded in the CRF if voluntarily shared by the patient. In case of study termination, the investigator must ensure that the patient returns the activity tracker, and that no subsequent activity tracker will be shipped to the patient.

Specifically, the following termination criteria apply:

- Patients not eligible for treatment with 3D regimen in accordance with the Swiss product label and according to the investigator's judgment will discontinue study participation.
- Patients who discontinue treatment with 3D regimen or who do not wear the activity tracker for at least 3 weeks before each visit will be withdrawn from the study. In case the decision to discontinue treatment with 3D regimen was taken before or during a routine clinic visit, this visit will be considered the last study visit. The last dose of treatment of 3D regimen will be recorded in the CRF.
- Patients with an average FSS score < 4 at visit 2 will discontinue the study.

Following discontinuation of the study, the patient will be treated in accordance with the investigator's best clinical judgment.

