## **9.7 Data Analysis**

All data will be analyzed by descriptive statistical methods.

Quantitative data (e.g. the primary variable) will be analyzed by the statistical parameters valid N, missing N, mean, standard deviation (SD), and selected quantiles: minimum (0%), lower quartile (25%), median (50%), upper quartile (75%), and maximum (100%). If indicated by the data, an additional frequency distribution will be supplied after appropriate grouping of data.

Qualitative (e.g. achievement of SVR12 (yes/no)) and categorical variables (e.g. individual items of the FSS) will be presented by (absolute and relative) frequency distributions.

The primary variable will be tested using the one-sample t-test (two-sided) on the 5% significance level.

Two-sided 95% confidence intervals will be provided for mean daytime physical activity, FSS and sleep efficiency by visit and for the changes between start of treatment and the respective follow-up visits. A 95% confidence interval for the proportion of patients achieving SVR12 will also be calculated.

The correlation between the physical activity (assessed by the activity tracker) and the fatigue score (assessed by FSS) will be investigated by visit and for the changes between baseline and follow-up visits, using Spearman's rank correlation coefficient.

Subgroup analyses will be provided for patients who achieve / do not achieve SVR12 after treatment with 3D regimen.

All statistical analyses will be carried out by means of the SAS® package (version 9.2 or higher).

Details of planned analyses will be described in a separate statistical analysis plan (SAP).

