5.2 Analysis Populations (ITT and mITT)

The statistical analyses will be performed for the intention-to-treat population (ITT) and the modified ITT population (mITT) as well. The ITT consists of all documented patients of the overall population with treatment as intended to protocol and received study medication at least once. Additionally, mITT consists of all patients of the ITT which take part at all five visits. For ITT and mITT descriptive and safety parameters will be analyzed. Primary and secondary endpoints will be analyzed for mITT.

6 Statistical Methods

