6.3.2 Secondary Endpoints

For the secondary endpoints „change of FSS between baseline, during and after 12 weeks“ the difference between baseline and the respective follow-up visits will be calculated and

shown with 95% confidence intervals (95%-CI). This analysis will also be performed for the parameters daytime activity and sleep efficiency.

Furthermore for daytime activity, FSS and sleep efficiency 95%-CI will be provided at baseline, during the study and after 12 weeks.

The correlation between mean daytime physical activity and FSS will be analyzed for each visit and for the changes between baseline and follow-up visits using Spearman's rank correlation coefficient.

The proportion of patients achieving SVR12 will be calculated and shown with 95 % confidence interval.

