6.3.3 Subgroup Analyses

According to the HEMATITE study protocol (version 1.0, 09/20/2016) „subgroup analyses will be provided for patients who achieve/do not achieve SVR12 after treatment with 3D regimen“. These analyses will be performed for ITT and mITT.

Daytime activity, FSS and sleep efficiency will be compared between following groups:

- Patients with Ribavirin vs. patients without Ribavirin at visit V2, V3, V4 and V5.
- Women vs. men at each visit.
- Patients with different fibrosis stages (F0, F1, F2 or F3) at each visit.
- Patients with different age categories (median split) at each visit.

Additionally for patients with GT1a vs. patients with GT1b FSS will be compared at each visit.

All statistical analyses will be performed by SPSS® for Windows, version 22.0.

7 Time table

The following temporary periods of time are planned:

| | |
|----------------------------------|------------------|
| Last patient out | April 2018 |
| Data input until | May 2018 |
| Cleanfile | June 2018 |
| Statistical analyses | Juli/August 2018 |
| Integrated Clinical Study Report | September 2018 |

Deviations from this plan because of unexpected occurrence are possible.

8 Planned tables for the statistical part

| Number | Items | Database/Variables |
|--|--|--|
| 1 Information to the study course | | |
| 1.1 | Enrolled/dropped out patients | Database 1 – Visit 1 (Day -28) |
| 1.2 | Study visits and study termination | Database 1 – Visit 1 (Day -28) – Visit 5 (Day 168, SVR12) |
| 1.3 | Patient eligibility criteria | Database 1 – Visit 1 (Day -28) |
| 2 Patients baseline characteristics | | |
| 2.1 | Demographics | Database 1 – Visit 1 (Day -28) |
| 2.2 | Medical history | Database 1 – Visit 1 (Day -28) |
| 2.3 | Fatigue severity scale (FSS) | Database 1 – Visit 1 (Day -28) |
| 2.4 | HCV history | Database 1 – Visit 1 (Day -28) |
| 2.5 | Vital signs | Database 1 – Visit 1 (Day -28) |
| 2.6 | Laboratory | Database 1 – Visit 1 (Day -28) |
| 2.7 | Smoking/alcohol status | Database 1 – Visit 1 (Day -28) |
| 2.8 | Activity tracker | Database 2 – Tracker data |
| 2.9 | Concomitant medication | Database 1 – Visit 1 (Day -28) |
| 3 Patients characteristics during study | | |
| 3.1 | Activity tracker | Database 2 – Tracker data |
| 3.2 | (S)AEs and concomitant medication | Database 1 – Visit 2 (Day 1) – Visit 5 (Day 168, SVR12) |
| 3.3 | Fatigue severity scale (FSS) | Database 1 – Visit 2 (Day 1) – Visit 5 (Day 168, SVR12) |

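### The visit 2 FSS cut-off selects on the score that serves as FSS baseline, so FSS is expected to fall afterwards even if treatment does nothing

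*Protocol*

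**What the plan says.** **The removal rule.** Protocol 9.1.1 (Questionnaire) states: "Patients with an average FSS score < 4 at visit 2 will discontinue study participation". Protocol 9.1.4 repeats it: "Patients with an average FSS score < 4 at visit 2 will discontinue the study". Entry also requires FSS of at least 4. A routine score up to three months old at V1 may be used, yet the FSS is also completed at V1. Which of these scores qualifies the patient is not stated.

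**The reference visit for change.** Protocol 9.7 gives confidence intervals "for the changes between start of treatment and the respective follow-up visits". The table in Protocol 9.1.2 starts treatment at V2 (Day 1). The same section correlates FSS with activity "by visit and for the changes between baseline and follow-up visits", without naming the baseline visit. SAP 6.3.2 says that "the difference between baseline and the respective follow-up visits will be calculated and" shown with 95% intervals, again without naming it. The table plan in SAP 8 puts V1 FSS under baseline characteristics (item 2.3) and V2 to V5 FSS under characteristics during the study (item 3.3).

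**The analysis set and the caveats.** SAP 5.2 analyses secondary endpoints in the mITT, where "mITT consists of all patients of the ITT which take part at all five visits". SAP 3.1 provides no replacement for missing FSS. Protocol 9.9 discusses confounding and missing data but not regression to the mean.

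**The concern.** Keeping only patients whose V2 score is 4 or more retains some whose score was high that day by chance and drops some whose score was low by chance. V3, V4 and V5 carry no such cut. Measured from V2, the average change is therefore tilted downward before any drug effect.

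The research question in Protocol 8.1 asks whether treatment reduces fatigue, and FSS change is a named secondary variable (Protocol 9.3.2). The tilt points towards the hoped-for answer. An interval lying wholly below zero would be read as improvement, and this design has no control group against which to check it.

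The unnamed baseline adds a smaller problem: two analysts could compute different FSS changes from the same plan.

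**Working it through.** **The plan's own figure.** None exists for FSS. The only sizing statement (Protocol 9.5) concerns the activity endpoint: 100 patients, effect size 0.29, two-sided 5% one-sample t-test, 80% power. It reproduces at 81.9% and does not bear on this point.

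**Inputs.** From the documents: entry at FSS of at least 4, removal at V2 below 4, FSS at V1 to V5, a 1 to 7 scale. Assumed, because the documents are silent: zero true change, unselected mean 4.0 to 5.5, SD 1.4, between-visit correlation r of 0.7 to 0.9, and n = 80 analysed.

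**Formula (r the same between all visits, V1 used for entry).** The regression of V5 on V1 and V2 gives each a coefficient r/(1+r). In retained patients V1 and V2 lie on average the same distance m above the unselected mean. Hence

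E(V5 - V2) = 2r·m/(1+r) - m = -m(1-r)/(1+r),

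which is negative for every r below 1.

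**Hand check at mean 4.0**, where the cut sits at the mean:
- P(both scores at least 4) = 1/4 + arcsin(r)/(2π), and m = SD(1+r)/[2√(2π)·P].
- So E(V5 - V2) = -SD(1-r)/[2√(2π)·P].
- r = 0.8: P = 0.3976; change = -(1.4 × 0.2)/(5.013 × 0.3976) = -0.140. Share removed at V2 = 1 - 0.3976/0.5 = 20.5%.
- r = 0.7: P = 0.3734; change = -(1.4 × 0.3)/(5.013 × 0.3734) = -0.224.

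**Simulation over the range** (scores clipped to 1-7, no true change), mean V5 - V2:

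| Unselected mean | r = 0.7 | r = 0.8 | r = 0.9 |
|---|---|---|---|
| 4.0 | -0.224 | -0.140 | -0.064 |
| 4.5 | -0.169 | -0.106 | -0.049 |
| 5.0 | -0.121 | -0.077 | -0.034 |

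At mean 5.5, r = 0.8 to 0.9 gives -0.05 to -0.02. Rounding scores to ninths, as a nine-item mean requires, changes these only slightly (-0.10 at mean 4.5, r = 0.8).

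**Effect on the interval** (mean 4.5, r = 0.8, SD of change 0.81, n = 80):
- Standard error = 0.81/√80 = 0.0906, and 0.106/0.0906 = 1.17.
- The critical t is 1.99, so P(interval wholly below 0) ≈ Φ(1.17 - 1.99) = Φ(-0.82) ≈ 0.21. Simulation gives about 20%.
- Over the whole range the share is about 6% to 50%, against a nominal 2.5%.

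**What the V2 rule contributes.** At mean 4.5, r = 0.8, selection at V1 entry alone gives V5 - V2 of 0.000; adding the V2 rule gives -0.106. If the correlation with V5 is about 10% lower, the figures are -0.078 and -0.197. The rule causes all of the fall when correlation is constant; entry selection adds to it when correlation fades.

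**Correlation decaying with time.** At mean 4.5, with r of 0.8 at 29 days falling to 0.6 in the long run and V1 used for entry, the change is -0.15 at V3, -0.26 at V4 and -0.30 at V5.

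**V1 as baseline.** If V1 was the entry score, V5 - V1 equals V5 - V2 to within 0.005. If an earlier score was used, V5 - V1 is 0.00 with constant correlation, but -0.16 in the decaying case above (V5 - V2 there is -0.25).

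**V1-to-V2 change, before treatment.** With V1 entry, mean 4.5 and r = 0.8, it is -0.16 in all patients with both scores but 0.00 in retained patients. With entry on an earlier score, retained patients show a rise, of +0.02 to +0.22 over the models run. A table of retained patients alone would hide or reverse the drift.

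**The case against.** The case for leaving the plan alone is fair in several respects. FSS change has no planned test and is not itself a listed secondary objective; there FSS appears only through its correlation with activity. V2 is the likelier baseline: SAP 8 splits vital signs and laboratory values between V1 and later visits in the same way, so the table layout may mean nothing. SAP 5.1 and 6.2 already plan overall-population descriptives, which would show FSS at V1 and V2 including patients removed at V2. Protocol 9.9 already warns about interpreting treatment effects. With a mean well above 4 and a high correlation, the artefact is negligible.

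All of this limits the weight of the point and none of it removes the direction. The planned descriptives give the two visits separately, not the paired change. Regression to the mean is neither confounding nor missing data, so 9.9 does not cover it.

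A reader might infer more than the documents support:
- *That the five-visit mITT creates the bias.* It adds nothing to it. Patients removed at V2 have no later FSS, so no analysis set could give them a change.
- *That V1 as baseline avoids it, or that V1- and V2-based changes bound it.* The two are equal if V1 was the entry score, and both are biased downward if correlation decays. V1 is free of it only if an earlier score was used for entry and errors are exchangeable.
- *That the artefact must look like a progressive response.* Growth from V3 to V5 appears only under decaying correlation.
- *That the primary endpoint is compromised.* Its definition does not use FSS.

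**Conclusion.** The point holds. Followed as written, the V2 rule with V2 as the reference visit biases the FSS change downward. The direction needs only a stable population mean and retest correlation below 1. The size cannot be determined from the documents: about -0.02 to -0.22 points at V5 under the constant-correlation assumptions above, and larger if correlation decays. The baseline wording is a genuine inconsistency, but naming the visit does not by itself cure the bias. The consequence is confined to how a fall in FSS may be interpreted, so this is an inexpensive improvement that should be made and not a flaw in the main analysis.

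**What to change.** Leave unchanged who stays in the study; whether to keep the V2 rule is for the sponsor.

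1. Reconcile Protocol 9.7, SAP 6.3.2 and items 2.3 and 3.3 of SAP 8. In SAP 6.3.2 state: *Baseline FSS is the visit 2 (Day 1) score.* Show the changes from V1 beside those from V2 as a sensitivity analysis, described as disclosing the artefact and not as bounding it.
2. Add the paired V1-to-V2 FSS change with 95% interval in all overall-population patients with both scores, including those removed at V2, as the pre-treatment drift.
3. Name regression to the mean among the limitations, in the SAP or the study report, and do not attribute a fall in FSS to treatment without that caveat.

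The scores are already collected at both visits, and the SAP is to be signed before database closure, so this can be done at SAP stage. The cost is two extra tables, a few sentences and a more cautious FSS conclusion. The artefact is disclosed, not removed.
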